### **6.6.3. Deaths**

All deaths on study will be listed along with the cause for death.

### **6.6.4. Consolidated AEs**

Given the high level of granularity of the MedDRA dictionary, clinically identical or synonymous PTs reported under different terms in the database, in addition to being reported separately, will also be consolidated in a separate summary. The list of consolidated AE categories will be reported in the clinical study report.

### **6.6.5. Immune-mediated AE**

Potential immune-mediated AE, such as colitis, pneumonitis, endocrine and hepatic events will be summarized.

### **6.6.6. Adverse Events of Special Interest**

Adverse events of special interest (AESIs) are AEs thought to be potentially associated with the study treatment or the underlying disease per protocol. Therefore, aggregate or single AE terms including additional medical interventions for identifying for AEs possibly associated or possibly associated with the study drug were developed.

Adverse events of special interest are listed in the Investigator's Brochure. The MedDRA PTs that are grouped under each of the AESI terms will be provided.

### **6.6.7. Clinical Laboratory Evaluation**

Summary and change from baseline by cycle will be provided for selected hematology, chemistry, coagulation tests, and thyroid function parameters.

Hematology and chemistry laboratory values will be graded according to CTCAE v4.03. The laboratory grade will be summarized by cycle and maximum post-baseline grade. Shift tables from baseline to worst post-baseline CTCAE grade will be generated.

Listing of abnormal laboratory events will be presented.

### **6.6.8. Vital Signs**

Vital signs (blood pressure, heart rate, temperature, and oxygen saturation), and weight will be summarized by cycle.

### **6.6.9. Electrocardiogram**

Electrocardiogram parameters including corrected QT interval (QTc) and change from baseline will be summarized by cycle and by treatment arm. QTc will be calculated based on Fridericia's formula (QTcF). Number and percent of patients for each QTc parameter for the following categories will be summarized:

- Absolute QTc <450, 450 to <480, 480 to 500, and >500 ms.
- QTc change from baseline 30 to <60 ms and  $\geq$ 60 ms.

### **6.6.10. ECOG Performance Status**

European Cooperative Oncology Group performance status will be summarized by cycle.

### **6.6.11. Utilization**

Utilization data will be summarized by category across arms. The following categories will be described:

- transfusions (on study treatment and during short-term follow up)
- hospitalizations (on study treatment and during short-term follow up)

For categorical variables, frequency and the corresponding proportions will be calculated.

## **6.7. Exploratory Analysis**

### **6.7.1. Pharmacokinetic Analysis**

Serum concentration data will be summarized. Descriptive statistics will include mean, median, range, and SD, as appropriate.

Additional PK and/or PK/pharmacodynamic (PD) analyses may be conducted at interim as well as on final data. These will be specified in a separate PK/PD analysis plan.

### **6.7.2. Biomarker Analysis**

Plans for biomarker analyses will be described separately.

### **6.7.3. Immunogenicity Analysis**

The treatment emergent (TE) ADA evaluable population will be defined within the Safety Population as those patients with both a baseline ADA test result and a postbaseline ADA test result. As a proportion of the TE ADA evaluable population, the number and frequency of the following will be tabulated by treatment group: TE ADA+ patients, and TE ADA+ patients with detected higher-tier assay results. Included in the same tabulation will be, as a proportion of the TE ADA evaluable population, the number and frequency of patients with ADA present at baseline, as well as patients with detected higher-tier assay results at baseline.

A summary will be provided of the number and percentage of patients who receive AM0010 reporting specific TEAEs (overall and by PT) by patient TE ADA status (TE ADA+, TE ADA-,

TE ADA Inconclusive, Patient not evaluable for TE ADA). The PT will be ordered by decreasing frequency in the TE ADA+ status group. The specific TEAE of interest are events in any one of the MedDRA Anaphylactic reactions Standardized MedDRA Query (SMQ), Hypersensitivity SMQ, Angioedema SMQ, Injection site reactions High Level Term (HLT), or Infusion site reactions HLT.

Additional immunogenicity analyses, to be presented in a standalone immunogenicity report in context with other studies of AM0010, will be described in a separate SAP.

#### 6.7.4. Crossover Patients

Patients in Arm 2 (pembrolizumab) who crossover to Arm 1 (AM0010 in combination with pembrolizumab) following documented disease progression will be analyzed accordingly if data warrants.

For patients who crossover to Arm 1 after documented disease progression on pembrolizumab, time to progression while on pembrolizumab will be compared to the time to progression following crossover, where the time to progression following crossover is defined as the time from time of crossover to the earliest documented disease progression. The last available tumor assessment before crossover will serve as the baseline for disease assessment post crossover. If the number of events permits, time to progression before and after crossover will be summarized descriptively using the Kaplan-Meier method.

Patients who crossover to the AM0010 in combination with pembrolizumab are censored at time of crossover (ie, AEs occurring during treatment with AM0010+pembrolizumab are excluded or control arm (pembrolizumab) patents). An exploratory safety analysis may be conducted for the crossover patients including all adverse events starting from the date of first dose of AM0010+pembrolizumab.

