7.8 Continued Treatment

7.8.1 Crossover

At the time of disease progression (as assessed by the Investigator) patients randomized to trial Arm 2 may crossover to study Arm 1 to receive AM0010 and pembrolizumab. When progressive disease is noted on the scan for an Arm 2 patient, no more than 21 days should pass before the patient crosses over to Arm 1. The scans and/or clinical assessment at crossover will be used as a new baseline to determine response or PD on Arm 1.

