^d Tumor assessment will be performed for all randomized patients every 9 weeks (±7 days) during the study treatment and during the first year from discontinuation of the study treatment, every 12 weeks (±7 days) during the second year, and every 16 weeks (±7 days) thereafter. Tumor assessment will be repeated until disease progression, death, or receipt of new anti-cancer therapy, or until study completion, whichever is first, whether or not study treatment was administered. A baseline tumor assessment is required at crossover.

^e ADA and PK samples will be collected on Day 1 of Cycles 1, 2, 3, 4, every fourth cycle thereafter, and at end of treatment visit, and at the follow-up visits 60 and 90 days after the last dose of study treatment.

^f Specific biomarker blood collection tubes may vary by time point. See the Lab Manual for details.

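### The before/after time-to-progression comparison in crossover patients (SAP 6.7.4) sets right-truncated times against ordinarily censored ones, so it cannot be read as an AM0010 effect in either direction

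*SAP*

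**What the plan says.** SAP 6.7.4 sits under Exploratory Analysis. It opens by saying that Arm 2 crossover patients "will be analyzed accordingly if data warrants". It then limits the population with the words "For patients who crossover to Arm 1 after documented disease progression on pembrolizumab". The contrast planned in that group is that "time to progression while on pembrolizumab will be compared to the time to progression following crossover". The second time is defined as "the time from time of crossover to the earliest documented disease progression". That definition does not name death as an event and gives no censoring rule. If there are enough events, "time to progression before and after crossover will be summarized descriptively using the Kaplan-Meier method". No test, alpha level or decision is attached, and no caveat either. The timing table in SAP 6.8 does not tie this analysis to a particular data cut.

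The baseline for the second period is worded in three places:
- SAP 6.7.4: "The last available tumor assessment before crossover will serve as the baseline for disease assessment post crossover".
- Protocol Appendix A, footnote d: "A baseline tumor assessment is required at crossover".
- Protocol 7.8.1: "The scans and/or clinical assessment at crossover will be used as a new baseline to determine response or PD on Arm 1".

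**The concern.** The two Kaplan-Meier curves would come from the same patients but would not estimate comparable quantities. A patient enters only after progressing on pembrolizumab and crossing over before the cut. An Arm 2 patient still controlled on pembrolizumab at the cut is absent from the first curve, not censored in it, so long pembrolizumab times are removed. The same patients are then followed forward after crossover with ordinary censoring, so long second-period times still count through the risk set. Crossover is also optional (Protocol 3.0), which adds self-selection, and no group shows how patients would have fared after progression on pembrolizumab alone.

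At stake is how a descriptive result is read. A longer second curve could be taken as activity in disease that had progressed on PD-1 blockade, and a shorter one as lack of activity or as harm. Neither reading would be justified.

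**Working it through.** SAP 6.7.4 gives no figure to reproduce. The check asks what the comparison shows when AM0010 does nothing.

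**Inputs from the documents.** Pembrolizumab median PFS 10.3 months (Protocol 1.1), used here for time to progression. Arm 2 size 50 (Protocol 3.2). Cuts about 6 and 12 months after the 100th patient (SAP 6.8). Three-year follow-up after the last randomization (Protocol 3.6). No more than 21 days from progression to crossover (Protocol 7.8.1).

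**Assumptions.** Exponential times. Uniform accrual over A months: 24 is implied by 60 months of trial duration (synopsis) minus 36 (Protocol 3.3), and 12 was also tried. All who progress before the cut cross over.

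**Step 1: truncation in closed form, ignoring the 21-day lag.** The hazard is λ = ln 2 / 10.3 = 0.0673 per month, and the cut falls F months after the last entry. The share of Arm 2 that has progressed by the cut is

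P = 1 − [exp(−λF) − exp(−λ(A+F))] / (λA).

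For m up to F, the median m of their pembrolizumab times solves 1 − exp(−λm) = P/2.

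- A = 24, F = 12: P = 1 − (0.446 − 0.089)/1.615 = 0.779. Then exp(−λm) = 0.611 and m = 7.3 months.
- A = 24, F = 6: P = 1 − (0.668 − 0.133)/1.615 = 0.669, and m = 6.0 months (just past F, where the formula is still accurate to this rounding).
- A = 24, F = 36: P = 1 − (0.089 − 0.018)/1.615 = 0.956, and m = 9.7 months.
- A = 12, F = 6: P = 1 − (0.668 − 0.298)/0.808 = 0.542, and m = 4.7 months.

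With an inert drug and an unchanged hazard, the true post-crossover median is 10.3 months. Kaplan-Meier recovers it because those times are only censored.

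**Step 2: simulation.** There were 60,000 Arm 2 patients per setting, with a 0–21 day lag and crossover only for progression within 24 months of randomization (an assumption suggested by the treatment cap in Protocol 3.0). Theta is the post-progression hazard divided by the pembrolizumab-period hazard. Entries are Kaplan-Meier medians in months, pembrolizumab period vs after crossover.

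| Accrual, cut | theta = 1 | theta = 1.5 | theta = 2 |
|---|---|---|---|
| 24 mo, 6 mo | 5.9 vs 10.4 | 5.9 vs 6.7 | 5.9 vs 5.1 |
| 24 mo, 12 mo | 6.9 vs 10.3 | 6.9 vs 6.9 | 6.8 vs 5.2 |
| 24 mo, 36 mo | 7.7 vs 10.3 | 7.6 vs 6.8 | 7.7 vs 5.1 |
| 12 mo, 6 mo | 4.6 vs 10.2 | 4.6 vs 6.7 | 4.6 vs 5.1 |

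The two steps agree closely at the 6- and 12-month cuts. At 36 months they differ (9.7 vs 7.7) because of the 24-month limit on crossover. Without that limit, simulation gives 9.6 vs 10.3, so most of the gap has closed.

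**Step 3: break-even hazard.** The post-crossover median is 10.3/theta, so the two medians coincide at theta = 10.3/m.
- 24-month accrual, 6-month cut: 10.3/5.9 = 1.75.
- 24-month accrual, 12-month cut: 10.3/6.9 = 1.49, or 10.3/7.3 = 1.41 without the 24-month limit.
- 12-month accrual, 6-month cut: 10.3/4.6 = 2.24.

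Above these values an inert drug looks harmful.

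**Step 4: robustness.** With gamma frailty of variance 1, 24-month accrual and theta = 1, the medians are 5.2 vs 8.4, 6.0 vs 8.7 and 6.7 vs 9.2 at the 6-, 12- and 36-month cuts. The apparent gain persists but is smaller at the 6- and 12-month cuts. A Kaplan-Meier curve of all Arm 2 patients with non-progressors censored returns 10.3 months. Nine-week scan intervals and deaths were not modelled.

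**The case against.** The strongest objection concerns direction. A reader might infer that the comparison will make AM0010 look beneficial even if it is inert. The documents do not support that. If AM0010 adds nothing, the second period is continued pembrolizumab in patients who have just progressed on it, and nothing in the protocol or SAP says their hazard stays the same. With 24-month accrual, a 1.5-fold rise removes the apparent gain at the 12-month cut and a doubling reverses it at every cut. This objection stands in full. It does not rescue the comparison, because the result then depends on an unmeasured hazard and on the cut-off date.

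A reader might also infer that crossover patients are all early progressors. Protocol 3.0 and 7.8.1 allow crossover at investigator-assessed progression with no early limit. Selection is on progression before the cut, and its effect shrinks with follow-up.

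The analysis is exploratory, conditional and descriptive, and this stands as a limit on importance. It does not remove the truncation, and the SAP states no limitation beside the comparison.

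Nor is this clearly the only efficacy information planned after crossover. Protocol 7.8.1 re-baselines these patients to determine response or progression, and Protocol 7.12 includes them in sampling for exposure-efficacy work.

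On the baseline, a reader might infer that patients could be left with no scan. That is largely answered. The SAP wording and Appendix A are compatible if the required crossover scan becomes the last available one, and Protocol 7.1 and 7.5 call for a scan at clinical progression. What remains is that 7.8.1 read alone would allow a clinical-only baseline, and SAP 6.7.4 read alone would allow an older scan.

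**Conclusion.** The concern holds in limited form. SAP 6.7.4 compares right-truncated times with ordinarily censored ones and has no concurrent control, so the contrast cannot be attributed to AM0010 in either direction. With an inert drug, an unchanged hazard and 24-month accrual, the spurious difference in medians is about 4 to 4.5 months at the 6-month cut and about 3 to 3.5 months at the 12-month cut. At 36 months it is between under 1 month and about 2.6 months, depending on whether crossover after 24 months is possible. At the 6- and 12-month cuts the difference cancels if the post-progression hazard is about 1.4 to 1.75 times higher. With 12-month accrual and the 6-month cut it takes a rise of more than 2-fold. These sizes rest on the assumptions listed above; the truncation itself follows from the SAP's own definition of the population. No primary or secondary conclusion is affected.

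**What to change.** In SAP 6.7.4, delete the before/after comparison. Report response and Kaplan-Meier time to progression after crossover as stand-alone descriptive results, and state how deaths and censoring are handled. If a pembrolizumab-period curve is shown alongside, base it on all Arm 2 patients with non-progressors censored, not on crossover patients only.

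The cost is one SAP paragraph and no new data. The loss is a within-patient contrast that has some appeal but no clear interpretation.

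Separately, and as a minor point, reconcile the crossover-baseline wording in SAP 6.7.4, Appendix A footnote d and Protocol 7.8.1 so that all three state the same rule. Which rule that should be is for the sponsor to decide.

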INTERIM ANALYSIS:	A planned interim analysis may be performed when the 50th randomized patient has been followed up for approximately 3 months. No statistical boundaries or alpha spending will be applied for this interim analysis as the primary purpose of this analysis is to assess safety and PK. At the time of interim data lock, all patients on study will continue on the study per protocol. See Table 6 for the schedule of analyses of key endpoints.
STATISTICAL METHODS: EFFICACY ANALYSES	All efficacy analyses will be based on the Intent-to-Treat (ITT) population, which includes all randomized patients regardless of whether the patient receives any study drugs or has any efficacy assessments. The primary efficacy endpoint is objective tumor response assessed according to RECIST v.1.1 criteria. The ORR will be summarized and compared using a Cochran-Mantel-Haenszel 2-sided test at a type I error rate of 10% stratified by tumor histology (squamous vs non-squamous.) Progression-free survival will be compared in the 2 randomized treatment arms using a 2-sided log-rank test, stratified by the tumor histology. Progression-free survival time will be summarized using the Kaplan-Meier method to estimate the median PFS and 95% confidence interval (CI). Overall survival will be summarized in the same manner as the PFS.
SAFETY ANALYSES	Safety Population includes all randomized patients who received any amount of study drug. Trial treatment exposure will be summarized. Adverse events will be summarized in terms of treatment-emergent events defined to be any event that begin or worsen in grade after first dose through 30 days after the last dose of trial drugs. Descriptive statistics of safety will be presented using NCI-CTCAE version 4.03 by treatment arm. All treatment-emergent AEs, due to any cause, treatment-related AEs, AEs leading to discontinuation from the trial treatments, SAEs, and drug-related SAEs will be tabulated using worst grade per NCI-CTCAE v4.03 criteria by system organ class and preferred term. On-trial lab parameters including hematology and chemistry will be summarized using the worst grade per NCI-CTCAE v4.03 criteria.

Table of Contents

CLINICAL TRIAL PROTOCOL	1
CONFIDENTIAL INFORMATION	1
PROTOCOL APPROVAL PAGE	2
PROTOCOL ACCEPTANCE PAGE	3
SUMMARY OF CHANGES	4
PROTOCOL SYNOPSIS	7
TRIAL GLOSSARY	21
1.0 BACKGROUND AND RATIONALE	24
1.1 Non-Small Cell Lung Cancer	24
1.2 AM0010 Background	25
1.2.1 AM0010 Mechanism of Action	25

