3.0 TRIAL DESIGN

This is an open-label, randomized, multicenter, Phase 2 trial in 100 adult male and female patients with treatment-naïve, Stage IV/metastatic NSCLC whose tumors are not known to have EGFR mutations or ALK rearrangements, but have high expression ($\geq 50\%$) PD-L1 as determined with an FDA-approved PD-L1 IHC 22C3 assay.

Patients will be stratified according to tumor histology (squamous vs non-squamous).

Patients will be randomized in a 1:1 ratio into 1 of 2 treatment arms (Figure 1).

[figure not shown]

Figure 1. Trial Design

Trial sites will provide best supportive care per institution's standard of care including concomitant medications.

Arm 1 and 2 treatment will continue in the absence of disease progression, unacceptable toxicity, or patient's withdrawal of consent. Patients will be treated with a maximum of 35 cycles of pembrolizumab every 3 weeks or 2 years, whichever is longer.

All radiological assessments will include at minimum, scans of the head, chest, abdomen, and pelvis.

At the time of documented disease progression (by Investigator assessment) patients in Arm 1 will be discontinued from the treatment period of the trial and continue on the follow-up period. At the time of documented disease progression (by Investigator assessment), patients in Arm 2 may crossover to receive treatment with AM0010 and pembrolizumab.

Confirmation of complete response (CR) or partial response (PR) is required. Confirmatory scans will be performed as follows:

- CR and PR criteria per RECIST v1.1 must be met again at least 4 weeks after initial documentation.

Patients with suspected pseudoprogression on scans in the absence of clinical deterioration should remain on trial treatments and be rescanned at 4 weeks or later as outlined in Section 7.6.

If progression is confirmed on follow up scan, then discontinue treatments and follow trial procedures for end of treatment and survival follow-up or procedures for crossover patients.

Scans will include head and CAPs and will be sent to the central imaging vendor for archiving and possible assessment at a later date. If clinical progression is suspected, all relevant clinical documentation is to be submitted to the central imaging vendor.

For patients who were randomized, but withdraw consent, survival (date of death) will be obtained by use of publicly available information.

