10.6.6 Adverse Events

Adverse events will be analyzed in terms of treatment-emergent AEs defined to be any AEs that begin or worsen in intensity after trial drug initiation through 90 days after the last dose of trial drug. All AEs will be coded based on MedDRA terms.

Descriptive statistics of safety will be presented using NCI-CTCAE v4.03 by treatment arm. All treatment emergent AEs due to any cause, treatment-related AEs, SAEs, treatment-related SAEs, and AEs leading to discontinuation from the trial treatments will be tabulated using the worst grade per NCI-CTCAE v4.03 criteria by system organ class and preferred

term. Additional summaries include AEs by intensity (Grade 1 to 4 or/and Grades 3 and 4). All AEs will be listed.

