### **6.1.2. Definitions and Conventions**

Study treatment refers to AM0010 + pembrolizumab or pembrolizumab.

The date of randomization is the date the patient was randomly assigned to AM0010 + pembrolizumab arm or pembrolizumab arm using the IWRS.

The date of **first** dose is the date of the first dose of any study treatments.

The baseline value of a safety assessment is the last value observed prior to the first dose.

The study day of a safety event or assessment will be calculated as:

- The difference between the date of the event or assessment and the date of first dose plus 1 for all events or assessments occurring on or after the day of first dose. For example, if an event occurs on 08 June 2018 and the date of first dose was 06 June 2018, the study day of the event is 3.
- The difference between the date of the event or assessment and the date of first dose for all events or assessments occurring before the day of first dose. For example, if an event occurs on 05 June 2018 and the date of first dose was 06 June 2018, the study day of the event is -1.

The study day of an efficacy event or assessment will be calculated as:

- the difference between the date of the event or assessment and the date of randomization plus 1 for all events or assessments occurring on or after the date of randomization.
- the difference between the date of the event or assessment and the date of randomization for all events or assessments occurring before the date of randomization.
- 1 month = 30.4375 days
- 1 year = 365.25 days

Unless otherwise noted, summaries of continuous variables will include a mean, median, standard deviation (SD), minimum, and maximum.

Unless otherwise noted, summaries of categorical variables will include the frequency and percentage (relative to the population being analyzed) of each category.

P-values will be rounded to 4 decimal places. P-values that round to 0.0000 will be presented as '<0.0001' and p-values that round to 1.000 will be presented as '>0.9999.' Confidence intervals (CIs) will be presented as 2-sided 95% CIs unless specified differently in specific analysis.

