**6.6.2. Adverse Events**

Adverse event terms will be mapped using MedDRA. Adverse events will be graded according to the National Cancer Institute (NCI) – A Common Terminology Criteria for Adverse Events (CTCAE) v 4.03.

Pre-existing conditions are defined as AEs that begin prior to the first dose of study drug.

A treatment emergent adverse event (TEAE) is defined as any AE that begins between the day of first dose and 30 days after treatment discontinuation (or up to any time if serious and related to study treatment), or any pre-existing condition that increases in CTCAE grade between the day of first dose and 30 days after treatment discontinuation (or up to any time if serious and related to study treatment).

Related AEs in patients treated with AM0010 in combination with pembrolizumab are defined as either related to AM0010 or related to pembrolizumab or both AM0010 and pembrolizumab.

The following TEAE/serious adverse events (SAE) outputs will be produced:

- a. overview of TEAEs
- b. summary of TEAEs by Preferred Terms (PTs) (all grade and grade  $\geq 3$ )
- c. summary of TEAEs by System Organ Class (SOC) and PT (all grade and grade  $\geq 3$ )

- d. summary of TEAEs by PT and Maximum Grade
- e. listing of SAEs
- f. summary of SAEs by SOC and PT (all grade and grade  $\geq 3$ )
- g. listing of TEAEs leading to study treatment discontinuation

Summaries b, c, d, and f will be produced for the related TEAEs/SAEs.

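### Arm 2 AE observation stops at crossover, but AEs are tabulated as crude percentages that adjust neither for that cut nor for unequal time on treatment

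*SAP*

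**What the plan says.** - **Cut at crossover.** SAP 6.7.4: "Patients who crossover to the AM0010 in combination with pembrolizumab are censored at time of crossover". AEs on the combination are left out of the control arm. They may appear separately: "An exploratory safety analysis may be conducted for the crossover patients including all adverse events starting from the date of first dose of AM0010+pembrolizumab".
- **Summary measure.** SAP 6.1.2: "summaries of categorical variables will include the frequency and percentage (relative to the population being analyzed) of each category". The outputs in SAP 6.6.2 are an overview, summary tables and listings. Neither document plans an exposure-adjusted AE rate or a time-to-event AE analysis. SAP 6.6.1.1 summarises exposure but does not link it to AE incidence.
- **TEAE window.** SAP 6.6.2 counts "any AE that begins between the day of first dose and 30 days after treatment discontinuation", with no time limit for serious related events. The protocol synopsis also uses 30 days: "any event that begin or worsen in grade after first dose through 30 days after the last dose of trial drugs". Protocol 10.6.6 instead runs "through 90 days after the last dose of trial drug".
- **Arm 1 at progression.** Protocol 3.0: "patients in Arm 1 will be discontinued from the treatment period of the trial and continue on the follow-up period". Arm 1 AE observation therefore also ends soon after progression.
- **Timing of crossover.** Protocol 7.8.1 allows it only after progression and within 21 days.
- **Objective.** SAP 4.2 lists the safety and tolerability profile among the items to be compared between arms.

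**The concern.** Censoring has a meaning for a rate or a cumulative-incidence curve. In a crude percentage a shortened observation period simply leaves less time for an event to be counted.

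Two things make observation time unequal here. First, a patient who crosses over loses most or all of the post-treatment tail of the TEAE window, while an Arm 1 patient who progresses keeps it. The open-ended clause for serious related events widens this, since it stays open for Arm 1 and closes for Arm 2 patients at crossover. Second, time on treatment may itself differ. It is longer in Arm 1 if AM0010 delays progression, and shorter if toxicity ends treatment, because protocol 6.4 stops both drugs when one is stopped.

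At stake is the reading of the between-arm safety comparison. Part of an observed difference, in either direction, could reflect observation time and not toxicity.

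**Working it through.** The documents give no AE incidence, no expected crossover share and no estimate of this effect, so there is no plan figure to reproduce. The size must be modelled.

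**Inputs from the documents**
- Median time to progression on pembrolizumab: 10.3 months (protocol 1.1, PFS in the cited phase 3 trial).
- Crossover 0 to 21 days after progression (protocol 7.8.1).
- TEAE tail of 30 days (SAP 6.6.2, synopsis) or 90 days (protocol 10.6.6).
- Cut-off about 6 months after the last patient is randomized (SAP Table JZGC.6.3).
- About 50 patients per arm (protocol 3.2).

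**Assumptions**
- Uniform accrual over 12 months, so follow-up is uniform on 6 to 18 months.
- Exponential time to progression; 60% of Arm 2 progressors cross over.
- The same first-AE hazard h in both arms, 0.05 to 0.10 per month. The 12-month risk is 1 − exp(−12h), or 45% to 70%.

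**Formula.** Let W be a patient's AE observation time, always capped at the data cut-off.
- Arm 1, and Arm 2 without crossover: end of treatment plus 30 or 90 days.
- Arm 2 with crossover: progression plus 0 to 21 days.
- Expected crude percentage = 100 × E[1 − exp(−hW)].

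**Tail lost by a crossover patient.** 30 − 21 = 9 to 30 − 0 = 30 days under the SAP window; 90 − 21 = 69 to 90 − 0 = 90 days under protocol 10.6.6.

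**Hand check, 30-day window, equal progression.** About 54% of Arm 2 have progressed by cut-off, so 0.54 × 0.60 = 0.32 cross over. The mean tail lost is 30 − 10.5 = 19.5 days = 0.64 months. Averaged over the arm this is 0.32 × 0.64 ≈ 0.20 months (simulated mean observation 8.57 vs 8.37 months). With h = 0.05 and about 75% still AE-free at that point, the shift is 0.20 × 0.05 × 0.75 = 0.0075, or about 0.8 points.

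**Simulated Arm 1 minus Arm 2, percentage points (h = 0.05 and h = 0.10; true hazards equal)**

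| Scenario | Crossover | 30-day window | 90-day window |
|---|---|---|---|
| Median 10.3 months in both arms | 60% | 0.8 to 1.2 | 2.8 to 4.2 |
| HR 0.65 (Arm 1 median 10.3/0.65 = 15.8) | none | 3.2 to 4.3 | 2.3 to 3.0 |
| HR 0.65 | 60% | 4.0 to 5.6 | 5.0 to 7.1 |
| Equal medians, 20% of Arm 1 off treatment by 12 months for other reasons | 60% | −1.5 to −1.8 | +1.3 to +2.2 |

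Repeat runs with fewer draws differ by up to about 0.2 points.

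**Attribution.** At HR 0.65 with the 30-day window, 3.2/4.0 to 4.3/5.6, roughly 80% of the gap, is there with no crossover at all.

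**Wider ranges.** With equal medians, 30% to 100% crossover, 12-month AE risk 10% to 60% and follow-up of 6 to 24 months, the cut alone gives 0.04 to 2.9 points (30-day) and 0.3 to 7.7 points (90-day).

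**Does a rate repair it?** Under a constant hazard, first events per patient-month at risk were equal between arms in every scenario. That follows from the model. With a front-loaded hazard (Weibull shape 0.5, same in both arms, HR 0.65, 30-day window) the rate makes Arm 1 look about 4% to 6% safer than it is.

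**The case against.** The strongest reply is that the cut is right and its effect small. Without it, AM0010 events would be counted against the control arm. Arm 1 observation also ends shortly after progression, so under the SAP window only 9 to 30 days differ. A shift of about 1 point is half a patient in 50. The standard error of a difference is about 9 to 10 points: √(2 × 0.33 × 0.67/50) = 0.094 and √(2 × 0.53 × 0.47/50) = 0.100. The larger figures come mainly from longer treatment, a limit of crude percentages in any trial. No formal AE test is planned, and treatment duration and laboratory grades by cycle are reported. Protocol 9.3 also lets follow-up be shortened when new therapy starts, which can trim the Arm 1 tail.

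Most of this stands. It rules out three stronger readings that a reader might infer:

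- **That every crossover patient counts as AE-free.** AEs before crossover still count. Only patients with none are affected.
- **That Arm 1 must look more toxic.** The sign depends on relative time on treatment, and earlier stopping in Arm 1 can reverse it.
- **That the crossover cut explains a gap of 4 to 7 points.** Most of the 30-day gap is unequal exposure. The 90-day figures rest on a window that the SAP does not use.

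It does not remove the point. The arms are compared on safety, the documents disagree on the window, and summarising exposure separately does not adjust an AE percentage for it.

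**Conclusion.** The concern holds in a limited form. The AE tables take no account of the shorter observation of crossover patients or of unequal time on treatment.

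With equal hazards, equal time to progression and 60% crossover, the cut alone shifts the arm difference by about 1 point (30-day window) or about 3 to 4 points (90-day window). Unequal time on treatment matters as much or more. At HR 0.65 with no crossover and the 30-day window it gives about 3 to 4.5 points. If 20% of Arm 1 stop early, the net difference is about −1.5 to −1.8 points under the 30-day window.

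These sizes rest on the assumed crossover share, hazards, accrual and exponential times, none of which the documents give. The open-ended clause for serious related events is not modelled. The primary endpoint is not affected. This is a worthwhile, inexpensive addition to the safety analysis and no reason to abandon the cut.

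**What to change.** 1. Keep the cut at crossover and the crude tables.
2. Add to SAP 6.6.2, by arm, for any TEAE, Grade 3 or higher, SAE, related TEAE and AESI:
   - exposure-adjusted incidence: first events per patient-year at risk, with time ending at the event, the end of the TEAE window, crossover or data cut-off, whichever is first;
   - a cumulative-incidence estimate that treats crossover as the end of observation.
3. State that arm differences in crude percentages will be interpreted alongside these.
4. Reconcile the 30-day window (SAP 6.6.2, synopsis) with the 90-day window (protocol 10.6.6), so that one window governs the tables.

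**Cost.** One more set of tables from dates already collected. Items 1 to 3 need SAP wording only; item 4 also needs the synopsis and protocol 10.6.6 to agree. The rates assume a roughly constant hazard and can favour the arm observed longer when AEs come early. The cumulative-incidence estimate is there to cover that, so neither measure should be read alone.
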